A double blind, randomised, placebo-controlled trial will test the effects of a synbiotic intervention in over 10 to 14 months in 100 patients with NAFLD (n=50 per treatment group). (N.B It is expected that the effect of the intervention on primary and secondary end-points will be constant between 10-14 months, see below Plan of Investigation.)

The synbiotic to be used is fructo-oligosachharide with a degree of polymerization < 10 at 4 g/twice a day (two sachets a day) plus *Bifidobacterium animalis* subsp. *lactis* BB-12 at a minimum of 10 billion CFU/day (1 capsule a day). The synbiotic will be provided as a capsule for probiotics, and powder (in a sachet) for prebiotics, to stir into a cold drink (i.e. < 25 degrees). The placebo will also be provided in a capsule and as powder in a sachet, comprising a total of 4 g/twice a day of maltodextrin

daily. Consequently, the synbiotic and the placebo will be supplied in identical packaging. The synbiotic/placebo is to be consumed soon after mixing and certainly within two hours. The powder could also be spread on food.

Safety information

The following gastrointestinal manifestations have been reported after the consumption of synbiotics consumption: increased bloating, increased flatulence and increased regularity of bowel movements (53).

V. Primary outcome measures

Primary outcome measures will be:

- i. Liver fat determined by magnetic resonance spectroscopy;
- Serum hyaluronic acid (HA), serum amino-terminal pro-peptide of type III collagen (PIIINP) and tissue inhibitor matrix metalloproteinase 1 (TIMP-1) concentrations; and a composite liver fibrosis score generated from concentrations of these three analytes (75).
- iii. Gut microbiota composition determined by 16S rRNA, FISH and qPCR.

VI. Secondary outcome measures

- i. Liver fibrosis determined by transient elastography
- ii. Insulin and glucose concentrations and hepatic insulin sensitivity
- iii. Microvascular function
- iv. Plasma cardiovascular risk markers
- v. Adipose tissue and blood markers of metabolism and inflammation
- vi. De novo lipogenesis
- vii. Satiety and satiety factors

VII. Power calculation for effect of treatment with a synbiotic on liver fat

There is little published literature to date upon which to base a sample size calculation to test the effects of the synbiotic treatment on the primary end point of change in liver fat.

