- Each participant will have approximately 2 weeks, or as much time as they need, to decide upon their participation after initial discussion with the research team doctor or nurse. Consent will be obtained by a participating medical doctor or nurse within the research team.. Translators are provided by the NHS Trust for non-English speaking participants. Only adults able to understand the nature of adipose tissue biopsy will be recruited.
- We will use the UHS clinical code database containing patients with a diagnosis of NAFLD. This information will be sought from the UHS Information Team in accordance with UHS NHS policy.

Detail of randomisation procedure

- Participants will be block randomized according to standardized procedures (computerized randomization) by a person from within University Hospital Southampton or the University of Southampton who is not connected to the INSYTE study. Investigators will be blinded as to treatment allocation until cessation of the trial.
- Stratified randomization to either trial medication (synbiotic or placebo) will be used.

Participant compliance

Participants will be asked to return all used and unused sachets at their next study clinic visit and their final clinic visit. Compliance will be assessed as percentage of sachets used.

- Non-compliance will be defined as missed usage of sachets for more than 6 months (53) (consecutively) during the whole study and or missed usage of sachets for 3 months (consecutively) before the end of the study.
- We will consider as compliant, participants who have had one or two courses of broad spectrum antibiotics during the study period. Participants will continue the synbiotic treatment during the antibiotic therapy and we will extend the synbiotic treatment for at least 1 month (i.e. 12+2 months of active therapy) before the final visit.

If there is indication that participants are non-compliant with trial treatment during the trial they will be withdrawn.

Detail of follow-up of non-compliant subjects & withdrawal of subjects

- Participants will be withdrawn if they develop a serious chronic illness that affects their liver condition.
- Participants will be withdrawn if they require treatment with a known hepatotoxic drug.
- Participants will be withdrawn if they have more than two courses of antibiotic therapy that is
 recognized to influence gut microflora during the study.

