- ii. Measures of insulin sensitivity, body composition and other features of the metabolic syndrome that help provide an estimate of future risk of type 2 diabetes. Presence of diabetes mellitus.
- iii. Assessment of prevalent cardiovascular disease.
- iv. Diet.
- v. Alcohol consumption.
- vi. Quality of life indicators.

Inclusion criteria

- Both men and women
- Age > 18 years
- Liver fat diagnosed on normal clinical grounds including in most cases liver assessed by Kleiner scoring system (76) to classify severity, with no known aetiological factors for underlying liver disease (e.g. exclusion of hepatitis A, B & C, primary biliary cirrhosis, autoimmune hepatitis, haemochromatosis). Last liver biopsy will be within 3 years of recruitment to the study.
- Liver fat diagnosed by ultrasound, CT or magnetic resonance imaging (MRI) within 3 years in patients who also have either diabetes and/or features of the metabolic syndrome, without evidence of known aetiological factors for underlying liver disease (e.g. exclusion of hepatitis A, B & C, primary biliary cirrhosis, autoimmune hepatitis, haemochromatosis).
- Alcohol consumption ≤ 14 units / week for women ≤ 21 units / week for men (77).

Exclusion criteria

- Alcohol consumption ≥ 15 units /week for women and ≥ 22 units /week for men.
- Decompensated acute or chronic liver disease.
- A history of viral hepatitis, diarrhoea, diverticulosis, actively symptomatic irritable bowel syndrome, inflammatory bowel diseases, coeliac disease (seropositivity for antiendomysial immunoglobulin A antibodies; IgA EMA).
- Previous bariatric or other abdominal surgery.
- Continuous use of antibiotics that may change gut microflora, probiotics, within the 2 months preceding enrolment, or evidence of immunoglobulin A or immunoglobulin deficiency (both of which produce confounding effects during assessments of intestinal permeability and small intestinal bacterial overgrowth).
- The participants may not be able to have an MRI scan if their weight is above 155 Kg as this is the maximum weight capacity for the magnetic resonance imaging.

3. Milestones and plan

Months 0-18	Recruitment of cohort, baseline measurements and randomisation to active compound or to placebo (10-14 month intervention)
Months 10-12	Follow up measurements begin
Months 10-32	Follow up measurements completed
Months 32-40	Measurements and analyses of results

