N.B. Since a recent publication testing the effect of a synbiotic in a small number (n=34) of people with NASH showed a 69% decrease in liver fat on liver biopsy score over 24 weeks (53), we will treat participants for a minimum of 10 months treatment. To allow for a degree of patient choice in the timing of the end of study measurement appointments, participants will undergo end of study follow tests between 10 and 12 months after randomisation. Finally, if a participant has been treated with one or two courses (two courses is the maximum allowed) of antibiotic therapy during the 12 months of the trial treatment period, we will allow for an extra 2 months of trial medication to be given to allow for the gut microbiota to return to pre-antibiotic therapy levels, Thus, although the trial intervention period is 10-12 months, there may be occasional participants who will be treated with up to 14 months (maximum) of trial medication.

4. Data Protection & Confidentiality: policy

- Data will be recorded on CRFs and the Data Management team will enter and manage the data on a secure UHS networked file store. Patient data (e.g. pathology results) captured directly by UHS systems will be extracted and merged with CRF data. SPSS software will be used as the primary package for managing the data prior to statistical analysis. Double entry and cross validation techniques will be used to ensure the quality of the data.
- Source data will be stored in a secure research office at the Wellcome Trust Clinical Research Facility at University Hospital Southampton NHS Foundation Trust during the trial. After cessation of the study, records will be stored in a secure room at The Institute of Developmental Sciences (IDS) Building, University of Southampton, MP 887 Southampton General Hospital, [name], in accordance with adherence to Data Protection Act 1998.
- The investigator(s)/institution will permit monitoring, audits, for REC review and provide direct access to source data and documents.

IX. Clinical Tests

1. Liver fat measurement

Magnetic resonance imaging

Liver fat estimation by MR will be undertaken at baseline and at the end of the study by both MR imaging and MR spectroscopy where possible, as the techniques provide an estimation of liver fat using different methodologies. Both techniques are quick and non-invasive, and the total scanning time

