Biomarkers will be measured in plasma or serum or will be generated from an algorithm.

Change in gut microflora

Measurement

Gut microflora will be assessed by 16S rRNA, FISH and qPCR

Statistical analysis

There are three primary endpoints; change in liver fat, change in biomarkers and change in gut microflora.

For measurements of liver fat, biomarkers and gut microflora:

Multiple regression analysis will be used, with final visit measurement as the outcome, and baseline measurement and randomised treatment group as predictors.

For each measurement, a multiple regression analysis will also be performed adjusted for potential confounders.

Potential confounders include but are not limited to: Change in body weight

For all outcomes, the treatment effect with 95% confidence interval will be reported (regardless of whether statistical significance is met). This will allow discussion of whether the trial result is compatible with a clinically important effect.

When reporting results it will be acknowledged that care should be taken in interpreting results from several outcome measures, as some statistically significant findings are likely to result from chance alone; consequently, we will allow for multiplicity of testing when interpreting our results.

Analyses by intention to treat (ITT) and Per Protocol

Analyses will be undertaken by an intent-to-treat (ITT) analysis and per protocol.

1. The ITT analysis will include all patients with complete data (i.e. having baseline and end of study measurements) in the groups to which they were randomised (regardless of whether they were later found to be ineligible, a protocol violator, given the wrong treatment allocation or never treated). This analysis assumes that any missing data is missing at random (MAR), i.e. that there is no difference between missing and observed values, once adjusted for any baseline variables which predict for missingness.

In order to explore the effect of departures from the MAR assumption, sensitivity analyses will be performed (140).

This assumes that d= the mean of the missing data minus the mean of the observed data. Under MAR, d=0.

The value of d will then be varied in order to model different scenarios (i.e. that the patients who are lost to follow up have systematically worse outcomes), and we will report whether the significance of the main analysis is maintained in the sensitivity analysis.

All randomised participants will be accounted for in these analyses.

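### The antibiotic entry rule bars only continuous use, so the baseline sample of the gut-microbiota primary endpoint can fall inside the recovery period the protocol allows after an ordinary course

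*Protocol*

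**What the plan says.** **Entry.** Protocol section VIII.2 (Exclusion criteria) excludes "Continuous use of antibiotics that may change gut microflora, probiotics, within the 2 months preceding enrolment". Continuous is not defined. No other section sets an antibiotic-free interval before the baseline stool sample or postpones that sample after a course.

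**During the trial.** Three rules apply to ordinary courses:
- Section VIII.3 (Milestones and plan, N.B.): after one or two courses, "an extra 2 months of trial medication to be given to allow for the gut microbiota to return to pre-antibiotic therapy levels".
- Section VIII.1 (Participant compliance): after one or two broad-spectrum courses, "we will extend the synbiotic treatment for at least 1 month (i.e. 12+2 months of active therapy) before the final visit".
- Section VIII.1 (withdrawal of subjects): "Participants will be withdrawn if they have more than two courses of antibiotic therapy", where the therapy is of a kind known to affect gut flora.

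**Role of the endpoint.** Section V lists "Gut microbiota composition determined by 16S rRNA, FISH and qPCR" as a primary outcome. Appendix 1 (Statistical analysis) says "There are three primary endpoints; change in liver fat, change in biomarkers and change in gut microflora", and fits a regression "with final visit measurement as the outcome, and baseline measurement and randomised treatment group as predictors".

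**The concern.** The protocol protects the final stool sample against ordinary antibiotic courses but does not protect the baseline sample, and both enter the same primary comparison. If one or two courses disturb the flora enough to justify prolonging treatment before the final visit, a course that ended just before baseline should matter too.

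The clock is also tied to enrolment, which is not defined, whereas baseline measurements spread over visits 1, 2 and possibly 3 (section X). A course taken between enrolment and the stool sample would not delay that sample.

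Precision and interpretation are at stake. A disturbed baseline predicts the final value less well, and recovery to the usual state is recorded as change. Appendix 1 also plans to analyse and publish baseline data before trial completion, and those data would carry the same disturbance.

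**Working it through.** **1. Rules side by side**

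| Sample | Does one ordinary course trigger action? | Interval |
|---|---|---|
| Baseline (VIII.2) | No, only continuous use | 2 months before enrolment |
| Final (VIII.3) | Yes, one or two courses | 2 extra months of trial medication |
| Final (VIII.1) | Yes, one or two courses | at least 1 month, glossed as 12+2 months |

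A course ending a week before baseline falls inside the recovery period on either figure. The gap therefore does not depend on which figure is right.

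**2. Numbers the protocol gives.** Section VII has 50 per arm and 14% dropout: 50 × 0.86 = 43 evaluable per arm. Its power statement reproduces. The standard error is 62 × √(2/43) = 13.37; 40/13.37 = 2.99; Φ(2.99 − 1.96) = 84.9%, against the stated 85%. This concerns liver fat only and is untouched by the present point. I use only the 43.

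**3. Effect on residual variance.** The protocol gives no share of participants with recent courses, no size of disturbance and no baseline-to-final correlation. The following are assumptions:
- a share p has its baseline shifted by d SD, with 0.5 SD of extra noise;
- the undisturbed baseline-to-final correlation is ρ;
- the final value is undisturbed.

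Baseline variance: V = 1 + p(1−p)d² + 0.25p.
Residual variance: R = 1 − ρ²/V.
Ratio to the undisturbed case: R/(1−ρ²).

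| p | d | V | Ratio, ρ = 0.6 | Ratio, ρ = 0.7 |
|---|---|---|---|---|
| 2% | 1 | 1.025 | 1.01 | 1.02 |
| 5% | 1 | 1.060 | 1.03 | 1.05 |
| 10% | 1.5 | 1.228 | 1.10 | 1.18 |
| 10% | 2.5 | 1.588 | 1.21 | 1.36 |

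Worked case for the last cell: V = 1 + 0.09 × 6.25 + 0.025 = 1.5875; R = 1 − 0.49/1.5875 = 0.691; 0.691/0.51 = 1.36. That equals losing 1 − 1/1.36 ≈ 26% of the sample for this endpoint. At 20% affected with 1.5 to 2.5 SD shifts, the same formula gives ratios of 1.16 to 1.49.

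**4. Within-arm change from recovery alone.** The mean apparent change in each arm is p × d: 0.02 SD at 2% and 1 SD, 0.25 SD at 10% and 2.5 SD. It is expected equally in both arms.

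**5. Chance imbalance.** Suppose one arm has 3 more affected people than the other. The adjusted estimate moves by slope × d × 3/43, with slope = ρ/V. Its standard error is √(R × 2/43). At 10% affected:

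| d | ρ | Slope | Movement (SD) | Standard error (SD) | Movement / SE |
|---|---|---|---|---|---|
| 1.5 | 0.6 | 0.489 | 0.051 | 0.181 | 0.28 |
| 1.5 | 0.7 | 0.570 | 0.060 | 0.167 | 0.36 |
| 2.5 | 0.6 | 0.378 | 0.066 | 0.190 | 0.35 |
| 2.5 | 0.7 | 0.441 | 0.077 | 0.179 | 0.43 |

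The movement is about 0.3 to 0.4 standard errors.

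**The case against.** The strongest reply is that this is loose drafting. The exclusion sentence is awkward and continuous is undefined. Its bracketed remark on confounding shows that the authors cared about the problem, so they may have meant any use. That is plausible, but staff apply the text as written, and the text lets a recent short course through.

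Second, the 2 months in section VIII.3 is added to the treatment period and is not timed from the end of a course. Section VIII.1 gives a different minimum. It is therefore not a settled washout that can simply be copied to baseline. This stands, and the two sections must be reconciled first.

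Third, Appendix 1 adds a second regression for each measurement, adjusted for potential confounders on an open list, and recent antibiotic use could enter there. This is partly right: baseline is the only covariate in the first model, not in every planned model. But antibiotic use is not named, and adjustment does not supply an undisturbed baseline.

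Fourth, the quantities in the variance calculation are all assumed, and with few people affected and a modest shift the loss is trivial. This also stands.

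A reader might infer that the treatment comparison is biased. It is not: the rule applies equally to both arms before randomisation. A reader might also infer that a few more affected people in one arm could imitate or hide a synbiotic effect. Step 5 of the working does not support that; such movement is ordinary sampling error already carried by the confidence interval.

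**Conclusion.** The point holds as a mismatch between the entry rule and the protocol's own handling of later courses, with a cost in precision. A person who has just finished an ordinary antibiotic course is eligible, and that person's baseline for a primary endpoint can be taken inside the recovery period the protocol allows elsewhere.

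The size is unknown. With up to 10% affected, the residual variance rise runs from about 1% to about 36%, depending wholly on the assumed share, shift and correlation. Part of any within-arm change would be recovery.

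The documents do not support extending the point to liver fat, which Appendix 1 calls the key primary endpoint and on which the trial was powered. It is worth correcting because the correction is cheap and the analysis cannot replace a baseline sample taken at the wrong time.

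**What to change.** Reconcile the antibiotic rules in sections VIII.1, VIII.2 and VIII.3:

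1. Settle one recovery period, resolving the conflict between at least 1 month (VIII.1) and 2 months (VIII.3). The choice is the sponsor's.
2. Reword the entry criterion to cover any course of antibiotics that may alter the gut flora, not only continuous use.
3. Keep probiotics explicitly in the sentence. The present criterion covers both in one phrase, and a careless rewording would drop the probiotic exclusion from a synbiotic trial.
4. Count the interval back from the baseline stool sample instead of from enrolment.
5. For affected candidates, postpone the baseline sample and randomisation until the interval has passed, so that they are not lost.

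The cost is a short amendment and a short delay for the affected candidates, within the 18-month recruitment window.

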- ii. To assess change in biomarkers with synbiotic treatment
- iii. To assess change in gut microbiota composition with synbiotic treatment

Secondary outcomes:

- i. Liver fibrosis determined by transient elastography
- ii. Insulin and glucose concentrations and hepatic insulin sensitivity
- iii. Microvascular function
- iv. Plasma cardiovascular risk markers
- v. Adipose tissue and blood markers of metabolism and inflammation
- vi. De novo lipogenesis
- vii. Satiety and satiety factors

Study site: University Hospital Southampton

Sample size and power

There is little published literature to date upon which to base a sample size calculation to test the effects of the synbiotic treatment on the primary end points. However, the study has been powered on the basis of the expected change in the key primary end point of a change in liver fat.

Based on the mean \pm SD of liver fat content in the sample of people with NAFLD who we recruited for our current randomised trial testing the effects of a n-3 fatty acid intervention in NAFLD in the WELCOME study (the Wessex Evaluation of fatty Liver and Cardiovascular markers in NAFLD with OMacor thErapy study); we estimate that the sample size would give 85% power to detect a 40% decrease in liver fat with the synbiotic intervention (allowing for 14% drop out). In the WELCOME study conducted over a longer period of intervention, 5% of the randomised cohort withdrew between randomisation and end of study measurements. In the WELCOME study the mean percentage fat content was 28.5%. Thus it is reasonable to expect that after treatment with the synbiotic, the mean percentage fat content would be 20% (giving a 30% decrease in liver fat). Liver fat content will be measured by MRS spectroscopy and this technique can reproducibly detect liver fat content as low as 5%.

One recent publication in people with NAFLD testing the effect of a synbiotic over 24 weeks in a small study showed a 69% decrease in liver fat (53).

Randomisation procedures

Patients will be randomised according to standardized procedures (computerized randomisation by a person from within University Hospital Southampton or the University of Southampton who is not connected to the INSYTE study). Stratified randomisation by age, sex and sub-study to trial medication or placebo will be used.

Data monitoring and interim analyses

Detailed analysis and publication of baseline data will be undertaken prior to trial completion by Profs, [name] and [name] and other investigators in discussion with the research nurses and BRC statistician. An independent data monitoring committee (IDMC) has not been set up for this trial, so there are no planned interim analyses of outcome data.

Procedures for data checking

Data will be checked for transcription and validation errors. Prior to any statistical analysis, all variables will be checked for number of missing values, impossible and improbable values. Impossible and improbable values for continuous variables will be defined by clinical opinion, other improbable values, defined as being more than three standard deviations from the mean, will also be checked. Errors in categorical variables will be identified as those with values missing from given terms in the Data

Dictionary. Inconsistencies will be referred to a named investigator by the data management team. Descriptive statistics will be calculated for all variables and distributional assumptions checked.

Trial analysis

Description of baseline data

All important variables collected at baseline will be summarised by treatment group. For continuous variables; means and standard deviations will be calculated. Distributions will be assessed using histograms and the normality assumption will be tested. When the data are not normally distributed medians and percentiles will be used to summarise data. Number and percentage will be calculated for categorical and binary data.

Primary endpoint

Change in liver fat and biomarkers from randomisation to end of study.

1. Change in liver fat (measured by MRS or IPOP MRI)

2. Change in biomarkers:

a) ELF score which is calculated using the following algorithm:

Score= $-7.412 + (\ln(HA)*0.681) + (\ln(P3NP)*0.775) + (\ln(TIMP1)*0.494).$

b) NAFLD fibrosis score which is calculated using age, hyperglycemia, body mass index, platelet count, albumin and AST/ALT ratio.

c) CK18 M30 and M65 as markers of apoptosis and necrosis

3. Change in gut microflora assessed by 16S rRNA, FISH and qPCR

Change in liver fat from randomisation to end of study

Measurement

Magnetic resonance spectroscopy (MRS) and/or MRI (IPOP) imaging will be used to determine the amount of liver fat as a percentage of the whole liver. This will be performed at baseline and at the end of study visit.

Change in biomarkers

Measurement

Biomarkers will be measured in plasma or serum or will be generated from an algorithm.

Change in gut microflora

Measurement

Gut microflora will be assessed by 16S rRNA, FISH and qPCR

Statistical analysis

There are three primary endpoints; change in liver fat, change in biomarkers and change in gut microflora.

For measurements of liver fat, biomarkers and gut microflora:

Multiple regression analysis will be used, with final visit measurement as the outcome, and baseline measurement and randomised treatment group as predictors.

For each measurement, a multiple regression analysis will also be performed adjusted for potential confounders.

Potential confounders include but are not limited to: Change in body weight

For all outcomes, the treatment effect with 95% confidence interval will be reported (regardless of whether statistical significance is met). This will allow discussion of whether the trial result is compatible with a clinically important effect.

When reporting results it will be acknowledged that care should be taken in interpreting results from several outcome measures, as some statistically significant findings are likely to result from chance alone; consequently, we will allow for multiplicity of testing when interpreting our results.

Analyses by intention to treat (ITT) and Per Protocol

Analyses will be undertaken by an intent-to-treat (ITT) analysis and per protocol.

1. The ITT analysis will include all patients with complete data (i.e. having baseline and end of study measurements) in the groups to which they were randomised (regardless of whether they were later found to be ineligible, a protocol violator, given the wrong treatment allocation or never treated). This analysis assumes that any missing data is missing at random (MAR), i.e. that there is no difference between missing and observed values, once adjusted for any baseline variables which predict for missingness.

In order to explore the effect of departures from the MAR assumption, sensitivity analyses will be performed (140).

This assumes that d= the mean of the missing data minus the mean of the observed data. Under MAR, d=0.

The value of d will then be varied in order to model different scenarios (i.e. that the patients who are lost to follow up have systematically worse outcomes), and we will report whether the significance of the main analysis is maintained in the sensitivity analysis.

All randomised participants will be accounted for in these analyses.

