A sample size of 50 in each group, with a 14% drop out during the study, will have 85% power to detect a difference of 40% in liver fat (in the treatment arm compared with the placebo), assuming that the common standard deviation is 62%, using a power calculation test with a 0.05 two-sided significance level. In our recent randomised controlled trial over a longer period of intervention, 5% of the randomised cohort withdrew between randomisation and end of study measurements. In this recent trial, the mean percentage fat content was 28.5% with a similar standard deviation to that presented above. Liver fat content will be measured by MRS spectroscopy and this technique can reproducibly detect liver fat content as low as 5%.

N.B. One recent publication in people with NAFLD testing the effect of a synbiotic over 24 weeks in a small study showed a 69% decrease in liver fat (53).

VIII. Plan of investigation

1. Recruitment

At University Hospital Southampton NHS Foundation Trust, potential participants with a diagnosis of non-alcoholic fatty liver disease (NAFLD) established as part of their attendance at hospital clinics, will be contacted by the research team. Contact will occur at their hospital clinic attendance or by letter of invitation from the research team.

Outside Southampton, at Poole Hospital NHS Foundation Trust, Portsmouth Hospitals NHS Trust, Royal Bournemouth and Christchurch Hospitals NHS Foundation Trust, Hampshire Hospitals NHS Foundation Trust, and the Isle of Wight NHS Trust, our collaborators (medical doctors responsible for the care of people with NAFLD) will act as 'post boxes' and inform potential participants about the study, providing people with a patient information sheet and asking them if interested to get in touch with the research team members at Southampton listed on the patient information sheet.

Because the centres outside Southampton are acting as 'post boxes' and not undertaking any research, completion of individual SSI forms may not be required for these sites because they are classified as site specific exempt.

Participant recruitment

- There will be no payment of participants but travel costs will be reimbursed.
- After discussion of their diagnostic liver biopsy test, or CT scan, or ultrasound, or MRI results, participants will be invited to participate in the research study, by direct contact from a member of the research team, or by letter of invitation.

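### Appendix 1 says the trial is powered on the expected change in liver fat, but its 85% power is for a 40% decrease while the expected change it gives is 30%

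*Protocol*

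**What the plan says.** Three statements stand together in the protocol's Appendix 1, Sample size and power:

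- The basis: "the study has been powered on the basis of the expected change in the key primary end point of a change in liver fat".
- The power: "we estimate that the sample size would give 85% power to detect a 40% decrease in liver fat with the synbiotic intervention", allowing for 14% drop-out and drawing on the mean and "SD of liver fat content in the sample of people with NAFLD who we recruited" for the sponsor's earlier n-3 fatty acid trial in NAFLD.
- The expectation: from that trial's mean of 28.5%, it is reasonable to expect that after synbiotic "the mean percentage fat content would be 20% (giving a 30% decrease in liver fat".

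Section VII gives the fuller power statement. There the target is "a difference of 40% in liver fat (in the treatment arm compared with the placebo", with 50 per group, 14% drop-out, a two-sided 0.05 level and "assuming that the common standard deviation is 62" per cent. It mentions neither the 20% nor the 30%.

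Both sections also cite a 69% decrease in a small published synbiotic study. Section VIII.3 (Milestones and plan) describes that result more fully: it "showed a 69% decrease in liver fat on liver biopsy score over 24 weeks", in 34 people.

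The analysis, in Appendix 1 under Statistical analysis, is a regression "with final visit measurement as the outcome, and baseline measurement and randomised treatment group as predictors".

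**The concern.** If the trial was powered on the change its investigators expect, the effect carrying the 85% and the effect described as expected should be the same. They are not. A 40% fall from 28.5% would end at 17.1%, not 20%. The section does not say why 40% was chosen over 30%, and gives no power for 30%.

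The two figures also differ in kind. Section VII defines the 40% as a difference between arms, whereas the 30% is a fall within the synbiotic arm. They can be compared directly only if placebo does not change.

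At stake is how the power statement is read. Liver fat is the only endpoint with a power statement, and as worded 85% can be taken as the chance of detecting what the investigators expect. That would mislead anyone judging the design or interpreting a null result.

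**Working it through.** **Inputs.** 50 per arm, 14% drop-out, SD 62%, two-sided 0.05 and a 40% target (section VII); means of 28.5% and 20% (Appendix 1). Evaluable per arm: 50 × 0.86 = 43. Assumption: the 40%, the 30% and the SD of 62% are on one scale.

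**Formula.** Standard error of the difference = SD × √(2/n) = 62 × √(2/43) = 13.37. Normal-approximation power = Φ(difference / 13.37 − 1.96). The noncentral t figure (84 df) is given beside it.

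**The protocol's own figure (40%).** 40/13.37 = 2.99; 2.99 − 1.96 = 1.03; Φ = 84.9% (t: 84.1%). The stated 85% reproduces with the unadjusted SD, so it contains no gain from baseline adjustment.

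**The expected change.** (28.5 − 20)/28.5 = 29.8%, so the stated 30% is right. A 40% fall would end at 28.5 × 0.60 = 17.1%.

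**Power at 30%.** 30/13.37 = 2.24; 2.24 − 1.96 = 0.28; Φ = 61.2% (t: 60.2%).

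**Smallest difference with 85% power.** 13.37 × (1.960 + 1.036) = 40.1% by the normal approximation; 40.5% by t, a fall from 28.5% to 16.9%.

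**Absolute scale.** If 62% is relative to the 28.5% mean, the SD is 0.62 × 28.5 = 17.67 points, the target 0.40 × 28.5 = 11.4 points and the expected fall 28.5 − 20 = 8.5 points. Power at 8.5 points is 60.7% (t: 59.7%), so the reading of the scale does not matter.

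**Drop-out.** At the 5% withdrawal reported for the earlier trial (47.5 per arm), power at 30% is 65.5% (t: 64.6%). With no drop-out (50 per arm) it is 67.7% (t: 66.8%).

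**Baseline adjustment.** The regression reduces the SD to 62 × √(1 − r²), where r is the baseline-to-final correlation. The protocol states no r, so these values are assumptions (43 per arm, t with 83 df):

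| Assumed r | Residual SD | Power at 30% | Power at 8.5 points |
|---|---|---|---|
| 0.5 | 53.7% | 72.6% | 72.1% |
| 0.6 | 49.6% | 79.2% | 78.7% |
| 0.7 | 44.3% | 87.4% | 87.0% |

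Reaching 85% at 30% needs r of about 0.67. The gain applies only if 62% is a cross-sectional SD, which the Appendix 1 wording suggests; an SD of change would not shrink in this way.

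**Placebo change.** As an illustration, if placebo also fell by an assumed 5 percentage points on the relative scale, the contrast would be 30% − 5% = 25% and unadjusted power about 46%. For a 30% fall on synbiotic to become a 40% contrast, placebo would have to rise, which the protocol does not suggest.

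**The case against.** The strongest reply is that nothing is miscalculated: both percentages are correct. On this view the sentence about the basis only singles out which of several primary endpoints drives the power, and the 20% figure may be there to show that liver fat will stay measurable by spectroscopy. A target difference need not equal the expected effect, and the cited 69% lies above 40%. The 60% is also fragile, being unadjusted, at the full 14% drop-out, and treating a within-arm fall as a contrast.

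Part of this stands. There is no computational error, and a target may legitimately differ from an expectation. Baseline adjustment could restore the power, so a shortfall for the planned analysis is not shown.

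The rest does not remove the conflict. If the sentence merely names the endpoint, the section still puts a 40% target beside a 30% expectation without linking them, and 30% is the only expectation it states for this trial. The 69% is not offered as the reason for 40%; it is a biopsy score, while this trial measures liver fat by magnetic resonance. Lower drop-out moves the unadjusted power only to 65–68%. The 85% is itself unadjusted, so the comparison with 60% is like for like. The within-arm caveat gives no comfort either, because a fall on placebo would make the contrast smaller than 30%.

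**Conclusion.** The concern holds. Appendix 1 claims the study is powered on the expected change, but the 85% belongs to a 40% decrease and the expected change is 30%. On the protocol's inputs without baseline adjustment, power is 84–85% at 40% and 60–61% at 30%.

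This rests on 43 evaluable per arm, an SD of 62% on the same scale as the effects, and no change on placebo. Under the planned regression, power at 30% would be about 73–87% for assumed correlations of 0.5–0.7. The fault is in the stated basis and the missing power at the expected effect; it does not establish that the trial is too small. It should be corrected because it changes what the 85% means to a reader.

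**What to change.** Edit only Appendix 1, Sample size and power.

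1. Replace the whole sentence giving the basis of the power. Suggested wording: *The study has been powered to detect a 40% difference in liver fat from placebo, which is larger than the 30% decrease expected on synbiotic.*
2. Add the power at 30%: about 60% unadjusted on the same inputs, together with the baseline-adjusted figure using the baseline-to-final correlation from the sponsor's earlier NAFLD trial, if available.
3. Add that the 30% is a within-arm fall and equals the difference from placebo only if placebo does not change.

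The sample size, section VII and the planned regression stay as they are. The cost is one sentence replaced, two added and one recalculation from the earlier trial's data. The downside is a less favourable stated power at the expected effect.
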